Building a Multidisciplinary Bridge Across the Quality Chasm in Thoracic Oncology

NCT02123797

03/09/2015

PCORI SPECIFIC AIM #3 (with process engineering sub-aim) RESEARCH PROTOCOL

Objective(s) of the study

The objective of this study is to provide rigorous evidence of the impact of multidisciplinary care on lung cancer patient outcomes. Multidisciplinary care is a model of care in which patients, their caregivers, and key specialists concurrently and directly evaluate the same patients in the presence of the patients and their informal caregivers, in order to develop evidence-based consensus care plans. Within the Baptist Memorial Health Care system, the Multidisciplinary Thoracic Oncology Program has two components: Primarily, the program is centered in a multidisciplinary clinic, wherein patients and their informal caregivers are seen by multiple specialists at a single appointment time; secondarily, the program includes a multidisciplinary conference, wherein all of the specialists potentially involved in lung cancer care discuss patients referred for presentation and make consensus recommendations for care. This study focuses primarily on the experience and outcomes of care delivered to patients evaluated in the multidisciplinary clinic. However, data from the conference may also be included in some aspects of the study. The goal is to improve the access and quality of thoracic oncologic care delivery within the Baptist Healthcare System.

The project is broken into three specific aims. The first specific aim has already been submitted separately and approved by the Baptist and University of Memphis IRBs. The second specific aim has been deemed exempt from IRB review as a quality improvement measure. The final specific aim is as follows:

Specific Aim #3 - Perform a prospective, matched cohort comparative effectiveness study of patients receiving serial vs. multidisciplinary care, with key patient-centered endpoints (survival, stakeholder satisfaction with the care experience, quality of life, timeliness and stage-appropriateness of care, quality of staging). Serial care is defined as the current system of linear, sequential, referral-based care delivery.

In an exploratory sub-aim, we will use computer simulation modeling provided by a process engineer to retrospectively and prospectively measure and optimize the efficiency of patient flow through the healthcare system.

Background

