We will begin Specific Aim #3 after a 3-month lead in phase, during which we ensure that all performance targets from Specific Aim #2 are being reliably measured. This aim will include administration of a series of patient, caregiver, and provider surveys as well as analysis of the quality benchmarks mentioned above. Specifically, we propose to perform a prospective, matched cohort comparative effectiveness study of eligible patients receiving care within the multidisciplinary environment versus matched controls concurrently receiving usual, serial care in the same healthcare system.

Eligibility criteria:

Multidisciplinary cases will have an untreated but biopsy-confirmed lung cancer diagnosed, preferably within 8 weeks of screening for study eligibility. Therefore, patients will still need either a staging evaluation or selection of first line therapy, the types of decision-making most often required in lung cancer care.

Controls will be selected from the pool of patients receiving usual ('serial') care within the same institution. Two serial care controls will be matched to each multidisciplinary care case. To be eligible for inclusion, a serial care patient must have an untreated biopsy-confirmed lung cancer, diagnosed preferably within an 8 week window surrounding the diagnosis of the case to whom he/she will be matched (4 weeks prior through 4 weeks after the case's diagnosis), and will be matched hierarchically based on several matching criteria: clinical stage, performance status, insurance status, race, and age range.

All multidisciplinary clinic patients will be screened for eligibility before their initial clinic visit. If a patient is determined to be eligible to participate in Specific Aim #3, they will be approached for consent to the study by the clinical research professionals during their initial visit.

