Patient feedback will be obtained on (a) satisfaction with care, and (b) quality of life (QOL), including both health-related QOL and depression/anxiety. Patient satisfaction will be measured using existing measures and measures created specifically for this study. The existing measure was originally developed for the Consumer Assessment of Healthcare Providers and Systems (Hays et al., 1999) and used in the Cancer Care Outcomes Research and Surveillance (CanCORS) Consortium (Ayanian et al., 2004; 2010), and assesses the interpersonal aspects of cancer care. Its 13 items load on three factors, including physician communication (e.g., “How often did your doctors listen carefully to you?”), nursing care (e.g., “How often were your nurses as helpful as you thought they should be?”), and coordination and responsiveness of care (e.g., “How often did the doctors, nurses, and other medical staff providing your care seem to work well together as a team?”). The three factors have been shown to have good internal consistency (Cronbach’s alphas ranging from 0.84-0.86 for the three factors for both lung cancer patients and surrogate respondents (family members) (Ayanian et al., 2010). We also will use single items from CanCORS to assess overall rating of care (“Overall, how would you rate the quality of your health care since your diagnosis of cancer?”) and perceived relative quality of care (“Would you say that you received medical care that was better than, about the same as, or worse than other patients with lung cancer?”). In addition, we developed items to tap aspects of satisfaction related to specific outcomes of this project, including satisfaction with the timeliness of care (e.g., “How satisfied are you with the length of time between learning that you might have cancer to being diagnosed?”), perceived obstacles to completing treatment, and perceived quality of care from specific care team members (e.g., oncologist, nurse navigator).

Patient QOL will be measured using two validated instruments. Health-related QOL will be measured with the Functional Assessment of Cancer Therapy – Lung Cancer (FACT-L) scale. The FACT-L is a widely

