We also will collect data on satisfaction with care and quality of life for the main informal caregiver (defined as the person who gives the patient the greatest amount of assistance and care on a day-to-day basis) for each patient who is enrolled in the study. Satisfaction measures will parallel the measures used with patients (described above). Caregiver health-related QOL will be assessed using the Short Form (36) Health Survey (SF-36; McHorney et al., 1994). The SF-36 is a widely used and validated measure of health-related QOL. It contains 36 questions and yields a psychometrically-based profile of physical and mental health in eight areas, including vitality, physical functioning, bodily pain, general health perceptions, physical role functioning, emotional role functioning, social role functioning, and mental health. The SF-36 has been validated in a number of populations, including caregivers (Bell et al., 2001, Machnicki et al., 2009) and is sensitive to change among clinical groups over time (Hemingway et al., 1997). Depression and anxiety will be assessed with the HADS, which also will be administered to patients (described above). Lastly, caregiver burden will be assessed using the Brief Assessment Scale for Caregivers of the Medically Ill (Glajchen et al., 2005), a validated 14 item scale that taps both negative (e.g., distress, lack of time) and positive (e.g., making the relationship with patient closer) aspects of caregiving.

For clinical provider feedback, we will use 2 instruments. The first instrument assesses provider satisfaction, focusing on the stated benchmarks of this study. It was developed specifically for this study, based on published surveys of provider experiences delivering cancer care (Taylor et al., 2012a, 2012b, Patkar et al., 2011; Shulman et al., 2013). The second survey is a multidisciplinary care workforce and workflow survey that seeks to identify obstacles to institutional multidisciplinary care.

The specified program benchmarks for survey administration and responses are as follows:

1. Ability to get satisfaction score responses from 60% of patients, caregivers and providers after interaction with the multidisciplinary care program;
2. Patient satisfaction scores corresponding to a 5 or 6 on a 6-point Likert-type scale (very satisfied or satisfied, respectively) in >80% of patients in surveys administered after initial clinic evaluation;

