3. Provider satisfaction scores corresponding to a 5 or 6 on a 6-point Likert-type scale (very satisfied or satisfied, respectively) in >70% of providers in surveys administered after each provider's active

interaction with the clinical program, either by direct participation (for participating providers) or after referring 5 patients into the program (for non-participating providers).

Certain multidisciplinary clinic staff (clinical research professionals) will be assigned with administering these surveys. These clinical research professionals will meet with patients during their initial visit to the Multidisciplinary clinic for the purpose of consenting patients to participate in the survey administration arm of the study and possibly to participate in the prospective comparative effectiveness study (Specific Aim #3). Once a patient/caregiver dyad gives consent to participate, surveys will be administered up to three times – once near the beginning of contact with the multidisciplinary clinic, a second time after a c. 3 month interval, and a third time after another c. 3 month interval (c. 6 months from the initial baselines survey). For clinical providers, surveys will be administered three times – once near the beginning of contact with the multidisciplinary clinic, and then two more times at 6 month intervals (after 6 and 12 months). Every attempt will be made to administer surveys to patients, caregivers, and clinical providers in person. If that is not possible, surveys may be taken over the phone, or by mail, but only if necessary. Patient dyads will be compensated with a \$10 Kroger gift card upon successful completion of the last round of surveys. Caregivers and clinical providers will not receive any financial compensation.

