Models for survival events: All patients will be followed up for at least one year from the beginning of the study (with a median of 1.5 year). The follow up time will be longer if the starting time is retrospectively tracked back to the date of first imaging diagnosis. Assuming t_i represents the time (days) from the first imaging diagnosis to death, $h(t_i)$ is the corresponding hazard function, the proportional hazard model is $\text{log}(h(t_i)) = \beta * G_i + \gamma X_i$. The exponent of β is the hazard ratio of survival between multidisciplinary program and controls. In addition, the proportional hazard assumption in the model will be examined visually by plotting - $\text{log}(\text{log}(\text{survival}))$ and time, and also by statistically testing by adding time interaction in the model. We will also visually compare the survival curve difference using Kaplan-Meier estimate and log rank test for curve difference between two groups. Finally, the Fine-Gray competing risk model will be used to compare lung cancer specific death.

Analyses for self-reported satisfaction with care and quality of life: patient, caregiver, and provider satisfaction scores are measured using survey methods. Surveys also are used to measure quality of life, including health related quality of life and depression/anxiety (in patients and caregivers) and caregiver burden (in caregivers only). For each measure, summary scores will be calculated according to the instructions in each survey instrument. Although the scores based on Likert scales can be treated as continuous variables, we will dichotomize the satisfaction scores as satisfactory (scores 5-6 on a 6-point scale) and unsatisfactory (scores 1-4), to correspond to our benchmark criteria. Descriptive analysis and logistic model similar to the previous analyses will be used.

Potential benefits to subjects/others.

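### The protocol does not assure a quality-of-life baseline taken before exposure and aligned between arms, and no starting-score adjustment is named for this non-randomised comparison

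*Protocol*

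**What the plan says.** - **Exposure.** Protocol, Objective(s) of the study: in the multidisciplinary clinic "patients and their informal caregivers are seen by multiple specialists at a single appointment time".
- **Consent.** Protocol, Eligibility criteria: for eligible clinic patients, "they will be approached for consent to the study by the clinical research professionals during their initial visit". Serial care patients are approached only after a matching clinic patient has consented.
- **Schedule.** Protocol, Effectiveness: surveys start "Once a patient/caregiver dyad gives consent to participate" and are given up to three times, "once near the beginning of contact with the multidisciplinary clinic, a second time after a c. 3 month interval", with the third "c. 6 months from the initial baselines survey". No instrument has a schedule of its own. Patients' satisfaction items, FACT-L and HADS share these waves, as do caregivers' satisfaction items, SF-36, HADS and burden scale.
- **Benchmark.** Protocol, program benchmarks for survey administration, item 2: patient satisfaction is scored "in surveys administered after initial clinic evaluation". No wave is named.
- **Analysis.** Protocol, Statistical analysis, on self-reported satisfaction and quality of life: "Descriptive analysis and logistic model similar to the previous analyses will be used". The SAP describes conditional logistic and stratified Cox models, using the matching variables as strata and adjusting for age, sex and histology.

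**The concern.** Satisfaction with the clinic can only be rated after the clinic visit. FACT-L, HADS, SF-36 and caregiver burden serve as a baseline only if they are completed before it. The protocol gives both kinds of form the same first wave without stating the order. Anxiety in particular may shift once a consensus plan has been given face to face, so the order could matter for HADS.

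Patient and caregiver quality of life is a listed endpoint, and the arms are formed by referral, not randomisation. If 3- and 6-month scores are compared without a starting score, differences that existed beforehand and that matching does not capture stay in the estimate. If they are compared using a starting score taken after the clinic visit, part of any early clinic effect is absorbed into the baseline. The text secures neither route.

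**Working it through.** The plan states no figure on this point, so the main check is to set the timing statements side by side.

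1. **Earliest possible wave 1, clinic arm.** Consent is sought during the initial visit and surveys follow consent, so no survey can predate that visit. Two orders remain: consent, forms, evaluation; or consent, evaluation, forms. Timing near the start of contact allows both. Surveys may also be taken by phone or mail where necessary, and a wave 1 collected that way would ordinarily fall after the visit.

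2. **What the labels imply.** The baseline label points to before the evaluation, and the satisfaction benchmark points to after it. Waves 2 and 3, at about 3 and 3 + 3 = 6 months, meet the benchmark wording in any case; wave 1 meets it only if given after the evaluation. Wave 1 is the natural candidate because it is the only wave close to the evaluation, but that is an inference.

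3. **Serial arm.** The only anchor for wave 1 is contact with the clinic, which these patients do not have. They are found from coded hospital lists and from lists supplied by the treating groups, so some may already have seen specialists when approached. They are untreated at eligibility, but nothing requires wave 1 to precede first treatment.

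4. **Adjustment.** The protocol's models carry a general term for confounders other than the matching variables. The starting score is not named there, in the survey analysis paragraph, or among the SAP covariates.

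5. **Size of the covariate's value.** Assume a linear model and a correlation r of 0.5 to 0.7 between wave 1 and later scores; the documents give no value. The residual variance fraction is 1 − r².
   - r = 0.5: 1 − 0.25 = 0.75; precision factor 1/√0.75 = 1.15.
   - r = 0.7: 1 − 0.49 = 0.51; precision factor 1/√0.51 = 1.40.

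6. **Size of the timing effect.** Suppose the visit shifts wave-1 HADS by d points in clinic patients only and wave 1 is taken afterwards. A change-from-wave-1 contrast moves by the full d. A contrast adjusted for wave 1 moves by about r × d, that is 0.5d to 0.7d, if score variances are similar across waves. The documents give no value for d.

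**The case against.** A reader might infer that clinic patients' baseline scores follow the intervention and that no pre-exposure baseline exists. The documents do not support this. The benchmark names no wave, and consent during a visit need not come after the evaluation. Some satisfaction items, such as those on the time from suspicion to diagnosis, can be answered before the specialists are seen. A pre-evaluation baseline is permitted; it is simply not required.

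A reader might also infer that a planned change-from-baseline analysis is biased by d. No such analysis is written, so that figure describes only what would happen if one were run. Nor does the 1.15 to 1.40 factor measure the cost of poor timing: a wave 1 taken after the visit would also give a precision gain if it correlates with later scores.

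The confounder term could include the starting score, and matching on stage, performance status, insurance, race and age range removes some pre-existing difference. Both points are fair, but the term is not specified for this purpose and the matching variables are not quality-of-life scores.

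A further fair point is that surveying clinic patients before any clinic specialist, and serial patients merely before treatment, could compare pre-consultation with post-consultation scores. The fix must therefore record and report timing in both arms.

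Finally, the survey instruments that the protocol says are attached, and part of the SAP, were not available for this review. A schedule given there cannot be excluded.

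**Conclusion.** The concern holds as a gap in assurance. On the available text, wave 1 may fall before or after the initial evaluation, has no defined anchor for serial patients, and is not named as a covariate in a non-randomised comparison. A pre-exposure quality-of-life baseline aligned across arms is not assured.

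The measurable part is the unused covariate: a precision factor of about 1.15 to 1.40, given a linear model and the assumed correlations. The cost of wrong order depends on the unknown d. It becomes relevant once wave 1 is used as a covariate, which is why order and adjustment should be settled together. Overall survival is the primary endpoint, so this affects a listed secondary outcome and not the main conclusion. It is worth correcting because the remedy is cheap. Confidence is medium, given the material not seen.

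**What to change.** 1. **Order the forms.** For clinic dyads, complete FACT-L, HADS, SF-36 and the caregiver burden scale at consent, before the specialists' evaluation where feasible, and the satisfaction benchmark items after it. For serial dyads, complete the quality-of-life forms at consent, before first treatment.
2. **Record timing.** In both arms, record when wave 1 was completed relative to first specialist consultation and first treatment.
3. **State the analysis.** Compare 3- and 6-month quality-of-life scores between arms as continuous outcomes, with the wave-1 score of the same instrument as a covariate, in addition to the planned matching strata and covariates.
4. **Sensitivity analysis.** Repeat the comparison excluding patients whose wave 1 followed the evaluation or the start of treatment.

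The SAP describes changes made after the study began. If wave 1 has already been collected, item 1 can no longer be applied to those patients, but items 2 to 4 can still be done as far as the recorded dates allow.

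The cost is a reordering of forms at a visit that research staff already attend, a timing record and one covariate. The downside is that consent and forms must fit before the first consultation and some will be out of order. Serial patients may already have seen specialists, so some baseline misalignment will remain and should be reported by arm.

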Patients who do not have a biopsy-confirmed lung cancer are excluded from this study.

Vulnerable populations

No vulnerable populations will be included in this study.

Length of study

Generally, this project is funded by a 3-year grant, which starts on February 3, 2014 and ends on February 2, 2017, with the possibility of extension by up to 1 year (February 2, 2018). However, because of the need to demonstrate program sustainability, we will continue to measure the quality benchmarks that constitute specific aim 2, as a key ongoing quality improvement exercise for the clinical multidisciplinary program. In addition, because of the primary endpoint, overall survival, it may be necessary to continue long-term follow up of patients for up to 5 years after enrollment of the final patient in specific aim 3, the comparative effectiveness study.

Number of study sites

Specific Aim #3 involves the Baptist Memorial Health Care Corporation system.

Number of subjects

Specific Aim #3 will match 150 patients undergoing care in the multidisciplinary clinic with up to 300 similar patients concurrently undergoing serial care for a total of 450 patients.

However, for the process engineering sub-aim, and to examine the domains of Reach and Adoption, all patients who receive lung cancer care from January 1, 2009, onward, and the clinical providers of lung cancer care, will need to be accessible for limited data abstraction.

Sample size calculation

150 multidisciplinary clinic patients matched 1:2 with 300 serial care patients = 450 patients for Specific Aim #3. The 150 multidisciplinary clinic patients will all be selected from the estimated 960 patients examined in Specific Aim #2. We powered the prospective comparative cohort study in Specific Aim #3 based on the survival analysis. Assuming power = 80%, alpha= 0.05, two sided test, mortality rate 40%, and hazard ratio 1.25, we estimate the total sample size 427 using Cox regression procedure in PASS 11. Since Baptist Health Care System manages >800 new cases each year, 300 of which are expected to be seen in multidisciplinary clinic, in practice, we conservatively expect to be able to recruit 150 cases from multidisciplinary clinic and 300 matched serial care controls (1:2 match) in 18 months.

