The above sample size estimate is based on our preliminary data. Among eligible patients, about 30% of cases are stage I/II, 30% stage III, and 40% stage IV. The corresponding one year mortality rates are 15%, 30% and 50%, respectively, and two year mortality rate is 30%, 50% and 70% respectively. Thus we estimated the range of the mortality rates from 30% to 50% in our mixed sample with a median follow up of 1.5 years. Furthermore, we estimate the relative difference in survival 20%-30% (i.e., hazard ratio between 1.2-1.3) between multidisciplinary program and controls, based on the hazard ratio reported in a study of early palliative care for stage IV lung cancer patients. Based on the above ranges, additional power analysis with a sample of 450 showed that, to reach the power 80% or above, hazard ratio is 1.3 for mortality rate of 30%; hazard ratio of 1.25 for mortality rate of 40%, and hazard ratio of 1.22 for mortality rate of 50%. A higher hazard ratio or higher mortality rate will yield larger statistical power. The sample size is adequate (power >90%) for detecting differences in rates of histologic confirmation of stage and selection of stage-appropriate treatment (20% absolute rate difference).

Statistical analysis

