Specific Aim #3 will require descriptive analysis. The percent of benchmark outcomes (Table 1) will be presented. We will use Chi-square test for categorical variables such as thoroughness of staging and treatment selection. T-tests will be used for continuous variables such as timeliness of care (days, logarithm transformed). All analyses may be stratified by race, gender, socio-economic status, and insurance status. Since we will measure the quality of care outcomes regularly during the whole study period, trend analysis will be conducted to monitor the change of these outcome measures. Computer simulation models will be used for pathway optimization analysis. In addition to descriptive analysis, statistical modeling will be the main tool to compare the quality of care and survival between multidisciplinary program and controls, adjusting for measured confounders. As noted, there are three types of outcomes: categorical outcomes such as thoroughness of staging, and receipt of stage-appropriate treatment; continuous outcomes such as timeliness of care, and survival events. In addition, since we will implement matching in the prospective cohort study by entry criterion, clinical staging, performance status, insurance status, race, and age range, matching analysis will be used. Specifically, in the multivariate models, we will use the conditional fixed effects logistic regression for binary categorical outcomes; fixed effects generalized linear model with Gamma distribution and logarithm link for timeliness of care; and fixed effects proportional hazard model for survival analysis. The matching pair indicates the fixed effect. These can be analyzed by commands such as *xtlogit* with *fe* option, or *stcox* with *strata* option in Stata.

Furthermore, because care delivery and treatment differ between patients with stage I/II and stage III/IV, stratified analysis will be conducted by staging groups. Both descriptive analysis and analytical models will be used. However, statistical power may be insufficient for the stratified analysis.

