### **Statistical Methods (Supplemental)**

The study was designed with overall survival as the primary endpoint. The design provided 80% power, with alpha of 0.05, to detect a hazard ratio of 1.25 between patients receiving multidisciplinary care and serial care. We targeted enrollment of 150 patients on the multidisciplinary arm and 300 patients on the serial care arm, matched by clinical stage (based on the initial diagnostic CT scan), performance status, insurance status, race, and age range. After initiation of the study, it was determined that the individual 1:2 matching strategy was not attaining high level matches within the allotted parallel time frame for the required number of subjects. To accommodate this change the following revisions were made to the statistical methodology. A frequency matching strategy was used based on the matching variables (age, sex, and histology were controlled for as a model covariate for better numerical efficiency). Crude comparisons between groups were made using standard univariate two sample methods. Comparative analyses were then conducted using matching variables as strata, per original design, with the strata now allowing multiple cases and controls per match group (frequency matching). Specifically, analyses were designed based on conditional logistic regression for each binary endpoint and stratified cox proportional hazards models for survival endpoints. Models were further adjusted to include age, sex, and histology in addition to the adjustment for strata described above. For each outcome, additional statistical models were evaluated controlling for matching variables as covariates in unconditional analyses. All analyses were conducted in SAS Version 9.4 (Cary, NC) with a type-I error rate of 0.05.

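### The 80% power stated for overall survival at a hazard ratio of 1.25 is wrong: 150 + 300 patients with 40% mortality give about 29%

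*Protocol*

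**What the plan says.** Overall survival is the primary endpoint. The SAP says so directly ("The study was designed with overall survival as the primary endpoint"), and the protocol says the cohort study was powered on the survival analysis.

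The protocol's *Sample size calculation* reads: "Assuming power = 80%, alpha= 0.05, two sided test, mortality rate 40%, and hazard ratio 1.25, we estimate the total sample size 427". The software named is the Cox regression procedure in PASS 11. Neither the standard deviation of the covariate nor its R-squared with other covariates is given.

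The same section then gives scenarios for 450 patients, each said to have at least 80% power: "hazard ratio is 1.3 for mortality rate of 30%; hazard ratio of 1.25 for mortality rate of 40%, and hazard ratio of 1.22" for mortality of 50%. The expected effect is stated as: "we estimate the relative difference in survival 20%-30% (i.e., hazard ratio between 1.2-1.3".

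*Number of subjects* sets the allocation: "match 150 patients undergoing care in the multidisciplinary clinic with up to 300 similar patients". Under *Models for survival events* the effect is the hazard ratio between the two care groups, so the exposure is a yes/no indicator.

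The SAP, *Statistical Methods (Supplemental)*, repeats the claim: "The design provided 80% power, with alpha of 0.05, to detect a hazard ratio of 1.25". The only warning about power, in the protocol's *Statistical analysis*, concerns analyses by stage group: "However, statistical power may be insufficient for the stratified analysis".

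**The concern.** A hazard ratio of 1.25 is a small effect, and 427 patients at 40% mortality supply only about 171 deaths. A two-group survival comparison normally needs several hundred deaths to detect an effect of that size.

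The figure governs how the main result is read. If the study is believed to have 80% power, a non-significant survival result looks like fair evidence against a benefit of the stated size. If the true power is near 29%, that result says little.

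**Working it through.** **Inputs.** From the protocol's *Sample size calculation*: two-sided alpha 0.05, power 80%, HR 1.25, mortality 40% (range 30% to 50%), 150:300 allocation, expected HR 1.2 to 1.3. With 450 patients, mortality of 30%, 40% and 50% means 135, 180 and 225 deaths.

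**Formula.** For Cox regression on a covariate X:

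deaths = (z_alpha/2 + z_beta)² / [Var(X) × (1 − R²) × (ln HR)²], and N = deaths / mortality.

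Here (1.960 + 0.842)² = 7.849. For a yes/no indicator split 1/3 : 2/3, Var(X) = (1/3)(2/3) = 0.222. R² is taken as 0, which favours the plan.

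**Trying to reproduce 427.** (ln 1.25)² = 0.0498. Deaths = 7.849 / (0.2222 × 0.0498) = 709, so N = 709 / 0.40, about 1,773. Other choices do not help:

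- 1:1 allocation: 631 deaths, N about 1,576
- one-sided test at 1:2: N about 1,398
- Freedman's formula: N about 1,590 at 1:1, and 1,659 to 1,923 at 1:2 depending on direction

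**What the stated figures imply.** Solving for Var(X)(1 − R²) = 7.849 / [deaths × (ln HR)²]:

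| N | HR | Mortality | Deaths | Implied Var(X)(1 − R²) |
|---|---|---|---|---|
| 427 | 1.25 | 40% | 170.8 | 0.923 |
| 450 | 1.30 | 30% | 135 | at least 0.845 |
| 450 | 1.25 | 40% | 180 | at least 0.876 |
| 450 | 1.22 | 50% | 225 | at least 0.882 |

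A yes/no variable has variance of at most 0.25, and R² can only lower the product. All four figures are therefore impossible for two groups at any allocation.

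One possible cause is that the group indicator was entered with an SD near 1 instead of 0.471. An SD of exactly 1 gives N of about 395; an SD of about 0.96, or an SD of 1 with R² of about 0.077, gives 427. The documents do not confirm this, and the finding does not depend on it.

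**Actual power.** Power = Φ( √(deaths × 2/9) × ln HR − 1.96 ).

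- N 450, HR 1.25, 40%: Φ(√40 × 0.2231 − 1.96) = Φ(−0.549) = 29%
- N 450, HR 1.30, 30%: 30%
- N 450, HR 1.22, 50%: 29%
- N 427, HR 1.25, 40%: 28%
- Corners of the plan's range: 17% (HR 1.2, 30%) and 46% (HR 1.3, 50%)
- All 450 patients dead: 45%, 61% and 75% at HR 1.20, 1.25 and 1.30

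The protocol says up to 300 controls. With 250, 200 or 150 controls, power at HR 1.25 and 40% mortality is 28%, 26% or 23%.

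**Detectable effects and precision.** The HR detectable with 80% power is exp(2.802 / √(deaths × 2/9)): 1.67, 1.56 and 1.49 at 135, 180 and 225 deaths. The smallest observed HR that reaches significance is exp(1.96 / √(deaths × 2/9)): 1.43, 1.36 and 1.32. At 180 deaths the expected 95% CI around 1.25 is 0.92 to 1.70.

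**Simulation checks.**

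- A log-rank simulation (8,000 runs per setting) gave 27.5% at HR 1.25 with 40% mortality, and 44.1%, 59.5% and 73.5% at HR 1.20, 1.25 and 1.30 with all patients dead.
- A second simulation (3,000 runs) used stage hazards from the stated two-year mortality and assumed follow-up uniform over 1 to 2 years, with a mean of 182 deaths. It gave 24.7% unstratified, 27.9% stratified by stage and 22.4% stratified by matched set.

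**Is the 40% input at fault?** No. The stated stage mix and mortality give 0.3 × 15% + 0.3 × 30% + 0.4 × 50% = 33.5% at one year and 0.3 × 30% + 0.3 × 50% + 0.4 × 70% = 52% at two years. A value of 40% at a median of 1.5 years is reasonable.

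**The case against.** The arithmetic is hard to dispute; the stronger objections concern scope and wording.

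- **Longer follow-up.** *Length of study* allows up to 5 years after the last enrolment, which would add deaths. An observed HR of 1.30 becomes significant at about 251 deaths (56% mortality), and with all 450 dead 80% power is reached at HR 1.32. So the statement that an observed 1.3 would be non-significant holds only for mortality of 30% to 50%, with a thin margin at 50% (1.32 against 1.30). Longer follow-up still does not give 80% power for any HR from 1.2 to 1.3.
- **29% is a formula value.** It ignores stratification and covariate adjustment, and the simulations run from 22% to 28%. This stands, and the correction should name the method. The SAP's frequency-matched strata with adjustment for age, sex and histology were not simulated. Nothing suggests they could lift power from under 30% to 80%.
- **A 20% to 30% difference might mean HR 0.8 to 0.7.** The protocol itself writes 1.2 to 1.3. Taking 0.70 (HR 1.43 inverted), power at 225 deaths is 71%, still short of 80%. With all 450 dead it would exceed 80%, so the all-dead statement applies only to the written range.
- **The SAP describes a past design.** It does, but it revised the matching and left the power claim unchanged, and readers will rely on that claim.

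The protocol's separate claim of over 90% power for staging and treatment selection is not affected.

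**Conclusion.** The concern holds. Power for the primary endpoint at HR 1.25 and 40% mortality is about 29%, not 80%, and the sample size needed is about four times the one stated (1,773 against 427). The required 709 deaths exceed the 450 patients planned. Across the plan's whole range of effects and mortality, power is 17% to 46%.

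This rests on a two-sided 5% test, a two-group indicator at 1:2, full enrolment, proportional hazards and no loss of information through stratification or adjustment. The implied-variance check is more general: the stated figures cannot arise from any two-group split.

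**What to change.** Add a dated correction to the protocol's *Sample size calculation* and to the SAP's *Statistical Methods (Supplemental)*, leaving the original target visible as history. Suggested wording:

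> With 150 patients in multidisciplinary care, 300 in serial care and 40% mortality (180 deaths), power to detect HR 1.25 at two-sided alpha 0.05 is about 29% by the Cox-regression events formula, without allowance for stratification or covariate adjustment. At 30%, 40% and 50% mortality, 80% power is available only for HRs of about 1.67, 1.56 and 1.49. This replaces the sample size of 427 and the three scenarios given as reaching 80%. Survival will be reported as an HR with 95% CI, and a non-significant result will not be read as evidence of no benefit.

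If fewer than 300 controls are enrolled, restate the power for the numbers reached. The longer follow-up that the protocol already allows would improve precision but cannot bring HR 1.2 to 1.3 to 80% power, so it is optional and not part of this correction.

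The cost is a wording change in two documents, with no added patients or follow-up. The stated power becomes much less favourable.
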